### 3.3.3. Risk-benefit Assessment

In the non-clinical setting, Debio 1347 exhibits high anti-tumour activity both in vitro and in vivo in cancers with amplification, mutation or translocation/fusion of the FGFR1, 2 or 3 genes, and cancers with overexpression of FGFR(s). This compound is regarded as an innovative therapeutic opportunity for cancer patients with genetic alterations in the FGFR1-3 genes or overexpression of the FGFR1-3 proteins.

In non-clinical safety studies of Debio 1347 in rats and monkeys, the principal target organs of toxicity were bone/cartilage, epithelial tissues and the kidneys. In addition, effects on lymphohaematopoietic tissues, liver and the gastrointestinal tract were observed. Mineralisation in multiple organs was also seen (such as trachea, stomach, kidneys, eyes in rats), with a broader range of organs and tissues affected in rats than in monkeys. On the other hand, periosteal changes occurred only in monkeys but not in rats. Except for thoracic deformity and mineralisation in multiple organs in rats, the changes seen in rats and monkeys in the 4-week repeated-dose toxicity studies either reversed or tended to reverse over the 4 week recovery period.

As a result, soft-tissue mineralisation, bone/cartilage effects, lymphohaematopoietic abnormalities, gastrointestinal and hepatic disorders, and ophthalmological disorders (mainly corneal mineralisation) are under close monitoring in the clinical setting. Subjects with phosphate/calcium homeostasis impairment are contraindicated. In addition, subjects with osteoporosis should be closely monitored. Investigators should reassess the risk-benefit ratio for each of their subjects.

Debio 1347 may have an in vivo phototoxic risk based on an in vitro phototoxicity test using a fibroblast cell line, where the compound was suggested as a phototoxic substance; and a whole-body autoradiography in rats after single oral dose of 1 mg/kg of [ $^{14}$ C] Debio 1347 suggesting a slower elimination rate of Debio

1347 from skin compared with blood. On the basis on these findings, subjects should avoid excessive exposure to sun/UV light.

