## 6.2. Exclusion Criteria

Any of the following would render a subject ineligible for inclusion:

1. History of hypersensitivity to any of the excipients in the Debio 1347 formulation (lactose hydrate, microcrystalline cellulose, croscarmellose sodium, hydroxypropyl cellulose, sodium lauryl sulfate and magnesium stearate).
2. Prior treatment with a FGFR1-3 selective inhibitor.
3. History and/or current evidence of ectopic mineralization/calcification, including but not limited to soft tissue, kidneys, intestine, myocardia, or lung, excepting calcified lymph nodes, lung nodules and asymptomatic vascular or cartilage/tendon calcifications.
4. Current evidence of clinically significant corneal or retinal disorder confirmed by ophthalmologic examination.
5. Chemotherapy, radiotherapy or small molecule anti-cancer agents within 2 weeks prior to initial dosing with Debio 1347 (3 weeks for immune checkpoint inhibitors).
6. Administration of any investigational agent within 2 weeks prior to initial dosing with Debio 1347 (3 weeks for immune checkpoint inhibitors).
7. Surgery requiring general anesthesia, except diagnostic biopsy or local procedure, within 3 weeks prior to initial dosing with Debio 1347 and/or if the subject has not fully recovered from the surgery.
8. Grade > 1 (National Cancer Institute Common Terminology Criteria for Adverse Events [NCI-CTCAE] v5.0) AEs or toxicities from previous treatments except:
  - a. Albumin ( $\geq 2.5$  g/dL is allowed).
  - b. AST and ALT in subjects with liver metastases ( $\leq 5 \times$  ULN is allowed).
  - c. Alkaline phosphatase (ALP) in subjects with bone metastases ( $\leq 5 \times$  ULN is allowed).
  - d. Any grade of alopecia is allowed.
  - e. Other Grade 1-2 clinically insignificant laboratory abnormalities are allowed.
9. Symptomatic or unstable brain metastases < 1 month (**Of note:** Subjects with asymptomatic stable and treated brain metastases are eligible).
10. Total corrected and/or ionized serum calcium  $\geq 1.5 \times$  UNL (corrected calcium =  $[0.8 \times (\text{normal albumin} - \text{subject albumin})] + \text{serum calcium level}$ ).
11. Gastro-intestinal disorders that could affect drug absorption (including, but not limited to, gastric resection, significant bowel obstruction, active ulcerative colitis, active Crohn's disease).
12. Concomitant treatment with a prohibited medication.

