### 9.1.3. Severity of Adverse Events

Adverse events will be graded according to the NCI-CTCAE v5.0 criteria.

Hyperphosphatemia, which is not included in the NCI-CTCAE v5.0, will be graded as follows:

1. Serum phosphate levels > ULN but < 5.5 mg/dL (~ equivalent to Grade 1);
2. Serum phosphate levels 5.5 - 6.9 mg/dL (~ equivalent to Grade 2);
3. Serum phosphate levels 7 - 9.9 mg/dL (~ equivalent to Grade 3, as this is the expected level at which soft tissue calcifications might develop);
4. Serum phosphate levels > 10 mg/dL with or without renal impairment (~ equivalent to Grade 4).

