### Appendix G: Hypercalcemia treatment

Subjects with asymptomatic hypercalcemia do not require immediate treatment if the calcium level remains < 12 mg/dL (3 mmol/L). However, the subject should be advised to avoid factors that can aggravate

hypercalcemia (such as thiazide diuretics, volume depletion, prolonged bed rest or inactivity, and a high calcium diet [ $> 1000$  mg/day]).

Adequate hydration (at least 6 glasses of water per day) is recommended to minimise the risk of nephrolithiasis.

- *Moderate asymptomatic hypercalcemia (calcium between 12 and 14 mg/dL [3 to 3.5 mmol/L]):* The decision to treat with saline hydration and bisphosphonates is at the Investigator's discretion.
- *Higher concentrations of calcium  $> 14$  mg/dL (3.5 mmol/L) or the presence of symptoms requiring more aggressive therapy.* In this case, it is suggested to treat with a three-pronged approach of isotonic saline (at an initial rate of 200 to 300 mL/hour that is then adjusted to maintain the urine output at 100 to 150 mL/hour), salmon calcitonin (4 IU units/kg) and concurrent administration of zoledronic acid (4 mg IV over 15 minutes) or pamidronate (60 to 90 mg over two hours).

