10.3.3 Clinical Laboratory Evaluations

Laboratory parameters include:

- Hematology: Complete blood count with differential, hemoglobin and platelet count.
- Chemistry: Total protein, albumin, indirect and total bilirubin, aspartate aminotransferase, alanine aminotransferase, alkaline phosphatase, electrolytes (sodium, potassium, calcium, and magnesium), serum phosphate, serum creatinine, creatinine clearance, uric acid, bile salts.
- Urinalysis: Red blood cells/hpf, white blood cells/hpf, casts/hpf, protein dipstick test.

For the purposes of summarization in both the tables and listings, all laboratory values will be presented in SI units. Both local and central laboratory values will be included in the analysis.

Hematology and chemistry parameters and corresponding changes from baseline will be presented as descriptive statistics by visit.

Shift tables based on the NCI-CTCAE v5.0 toxicity grading (and ad hoc grading criteria for hyperphosphatemia) will be presented for each hematology and chemistry parameter between baseline and the highest post-baseline NCI-CTCAE v5.0 toxicity grade or the highest post-baseline ad hoc grading criteria for hyperphosphatemia (including unscheduled assessment). The highest toxicity grade can either be above or below the laboratory standard normal range.

For hematology and chemistry parameters without a toxicity grading scale, the shift table will present directional shifts from baseline to above or below the laboratory standard normal range using the maximum increase and/or decrease observed post-baseline. Subjects who experienced both low and high laboratory test results will be reported in a separate “Low and High” column. “Low” and “High” column will represent the subjects having only low/high values respectively.

Boxplots of actual values and change from baseline will be presented by visit for selected hematology and chemistry parameters as relevant. Log transformation will be applied if necessary.

Urinalysis parameters will be summarized by visit using descriptive statistics. For categorical urinalysis parameters, missing data will not be considered as a category and the calculation of frequencies will use the number of non-missing observations. Results from the urinary pregnancy test will be listed.

Summary statistics will be presented for subjects with at least one post-baseline phosphate (phosphorus) level above 5.5:

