- Time from start of treatment to Phosphate level of 5.5mg/dL or higher, defined as [earliest date where phosphate \geq 5.5mg/dL] – [date of first administration of the study drug] +1

Category	Parameter	CTCAE Term	CTC Grading direction: Hypo (L)/ Hyper (H)/ No Grading (NA)	CTC Lab Test Unit	CTC Grade 0	CTC Grade 1	CTC Grade 2	CTC Grade 3	CTC Grade 4
Hematology	Hemoglobin	Hemoglobin increased	H	g/L	CHG <= 0	0 < CHG <= 20	20 < CHG <= 40	40 < CHG	
Hematology	Hemoglobin	Anemia	L	g/L	LLN <= aval	100 <= aval < LLN	80 <= aval < 100	aval < 80	
Hematology	Leukocytes	Leukocytosis	H	G/L	aval <= 100			100 < aval	
Hematology	Leukocytes	White blood cell decreased	L	G/L	LLN <= aval	3 <= aval < LLN	2 <= aval < 3	1 <= aval < 2	aval < 1
Hematology	Lymphocytes	Lymphocyte count increased	H	G/L	aval <= 4		4 < aval <= 20	20 < aval	
Hematology	Lymphocytes	Lymphocyte count decreased	L	G/L	LLN <= aval	0.8 <= aval < LLN	0.5 <= aval < 0.8	0.2 <= aval < 0.5	aval < 0.2
Hematology	Neutrophils	Neutrophil count decreased	L	G/L	LLN <= aval	1.5 <= aval < LLN	1 <= aval < 1.5	0.5 <= aval < 1	aval < 0.5
Hematology	Platelets	Platelet count decreased	L	G/L	LLN <= aval	75 <= aval < LLN	50 <= aval < 75	25 <= aval < 50	aval < 25
Hematology	Basophils		NA						
Hematology	Basophils/Leukocytes		NA						
Hematology	Eosinophils		NA						
Hematology	Eosinophils/Leukocytes		NA						

Category	Parameter	CTCAE Term	CTC Grading direction: Hypo (L)/ Hyper (H)/ No Grading (NA)	CTC Lab Test Unit	CTC Grade 0	CTC Grade 1	CTC Grade 2	CTC Grade 3	CTC Grade 4
Hematology	Ery. Mean Corpuscular Hemoglobin		NA						
Hematology	Ery. Mean Corpuscular HGB Concentration		NA						
Hematology	Ery. Mean Corpuscular Volume		NA						
Hematology	Erythrocyte Cell Morphology		NA						
Hematology	Erythrocytes		NA						
Hematology	Hematocrit		NA						
Hematology	Lymphocytes Atypical		NA						
Hematology	Lymphocytes/Leukocytes		NA						
Hematology	Monocytes		NA						
Hematology	Monocytes/Leukocytes		NA						
Hematology	Neutrophils Band Form		NA						

Category	Parameter	CTCAE Term	CTC Grading direction: Hypo (L)/ Hyper (H)/ No Grading (NA)	CTC Lab Test Unit	CTC Grade 0	CTC Grade 1	CTC Grade 2	CTC Grade 3	CTC Grade 4
Hematology	Neutrophils Band Form/Leukocytes		NA						
Hematology	Neutrophils/Leukocytes		NA						
Hematology	Reticulocytes		NA						
Hematology	Reticulocytes/Leukocytes		NA						

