- a. Absolute neutrophil count (ANC) $\geq 1,000/\text{mm}^3$ [$1.0 \times 10^9/\text{L}$].
- b. Platelet count $\geq 75,000/\text{mm}^3$ [$75 \times 10^9/\text{L}$].
- c. Hemoglobin $\geq 8.0 \text{ g/dL}$.
- d. Total bilirubin $\leq 2 \times$ upper normal limit (UNL) [biliary stent allowed]. A subject with an isolated elevation of indirect bilirubin is eligible.
- e. Aspartate aminotransferase (AST) and alanine aminotransferase (ALT) $\leq 2.5 \times$ UNL ($5 \times$ UNL in the presence of liver metastases).
- f. Calculated or measured creatinine clearance $\geq 30 \text{ mL/min}$ (creatinine clearance measured based on 24-hour urine collection should be considered to help assess eligibility).
- g. Serum phosphate $< 1.5 \times$ UNL.

10. Female subjects of child-bearing potential must have a negative serum pregnancy test (minimum sensitivity of 25 mIU/mL) at screening and be willing to practice the highly effective contraception methods listed below from the time of study entry up to 6 months after the last day of treatment:
 
 a. Intrauterine device (IUD) b. Intrauterine hormone-releasing system (IUS) c. Bilateral tubal occlusion d. Vasectomized partner e. Sexual abstinence if corresponds to usual and preferred lifestyle of subject. 
For hormonal contraceptives .
 
Of note:
 
 - Female subjects of non-childbearing potential are defined as either pre-menopausal with a documented tubal ligation or hysterectomy or post-menopausal with 12 months of spontaneous amenorrhea. - Female subjects of child-bearing potential must refrain from donating egg(s) during the clinical study and for 6 months after Debio 1347 discontinuation. - Male subjects must agree to use a condom from study entry and up to 6 months after the last day of treatment. The subject's female partner should use highly effective contraception methods, which may include hormonal contraceptives or any of the methods outlined above, during this period. - Male subjects must refrain from donating sperm during the clinical study and for 6 months after Debio 1347 discontinuation. 		

11. Available fresh tumor sample (preferably) or, if no fresh sample can be obtained, archived tumor sample (slides or block) for central analysis of FGFR status or retrospective central confirmation in case of local screening.
		

12. Life expectancy \geq 3 months.
		

Exclusion Criteria
		

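### SAP 10.3.3 times the rise of phosphate to 5.5 mg/dL without limiting the event to post-dose values and without separating subjects already at that level at baseline

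*SAP*

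**What the plan says.** SAP 10.3.3 introduces the summary with "Summary statistics will be presented for subjects with at least one post-baseline phosphate (phosphorus) level above 5.5". No unit is given. The definition that follows is "Time from start of treatment to Phosphate level of 5.5mg/dL or higher, defined as [earliest date where phosphate" is 5.5 mg/dL or more, less the date of first administration, plus 1.

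The level matters because Protocol 9.1.3 grades "Serum phosphate levels 5.5 - 6.9 mg/dL (~ equivalent to Grade 2", and Appendix E starts phosphate-binder treatment there. The SAP grading table puts the same boundary at 1.78 mmol/L.

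The entry limit is relative. Protocol 6.1 criterion 9g, repeated in SAP 13.6, requires "Serum phosphate $< 1.5 \times$ UNL", with no cap in mg/dL. Protocol 3.3.3 states "Subjects with phosphate/calcium homeostasis impairment are contraindicated", but gives no threshold.

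**The concern.** A time-to-onset summary should describe subjects who start below the level and reach it on treatment. Here the lead-in restricts which subjects are summarised, but the formula does not restrict which dates count, and neither sentence mentions baseline. A subject who enters at 6.0 mg/dL and stays there therefore contributes an onset time although nothing began on treatment.

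The SAP states such limits elsewhere: post-baseline values for the shift tables (10.3.3) and tumor size (10.2.4), start or worsening after first dose for TEAEs (10.3.2), and absence from the baseline tracing for ECG abnormalities (10.3.5.3).

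Protocol 3.3.2 lists hyperphosphatemia among the most common Phase I TEAEs and among those most often severe, so this summary is likely to be read.

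**Working it through.** **1. The plan's own cut-offs.** The conversion factor is 10/30.974 = 0.3229 mmol/L per mg/dL. The atomic mass is not in the documents, but their paired cut-offs imply 0.323 to 0.324.

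- 5.5 x 0.3229 = 1.776 (SAP 1.78)
- 7 x 0.3229 = 2.260 (SAP 2.26)
- 10 x 0.3229 = 3.229 (SAP 3.23)

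The figures reproduce, so the event threshold is the lower edge of the ad hoc Grade 2.

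**2. Does the entry limit reach 5.5 mg/dL?** It does when 1.5 x UNL > 5.5, that is, UNL > 5.5/1.5 = 3.67 mg/dL. The documents do not give the UNL. The Grade 1 band, "Serum phosphate levels > ULN but < 5.5 mg/dL (~ equivalent to Grade 1", implies only that it lies below 5.5. Over an assumed range:

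| Assumed UNL (mg/dL) | Entry allowed below (mg/dL) | Overlap with 5.5 or more |
|---|---|---|
| 3.5 | 5.25 | none |
| 4.0 | 6.00 | yes |
| 4.5 | 6.75 | yes |
| 5.0 | 7.50 | yes |

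Exclusion 8 does not reliably close the gap. It concerns toxicities from previous treatments, graded by NCI-CTCAE v5.0, which Protocol 9.1.3 says does not include hyperphosphatemia. Item 8e also tolerates clinically insignificant Grade 1-2 laboratory abnormalities.

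**3. The formula taken literally.** Time = (earliest date at 5.5 or more) - (first-dose date) + 1. Screening runs from Day -28 to Day -1.

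| First value at 5.5 or more | Time (days) |
|---|---|
| Screening, Day -28 | -28 + 1 = -27 |
| Screening, Day -14 | -14 + 1 = -13 |
| Screening, Day -1 | -1 + 1 = 0 |
| Day 1, pre-dose | 0 + 1 = 1 |
| Cycle 1 Day 8 (window 6 to 10) | 7 + 1 = 8 (6 to 10) |

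Unscheduled tests apart, any time of 1 or less comes from a pre-dose sample. Adding 1 to a pre-dose date also departs from SAP 9.2, which adds nothing before first dose.

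**4. The formula with post-baseline read in.** Times of zero or less disappear. A subject at 6.0 before dosing and still at 6.0 is first seen at the Cycle 1 Day 8 phosphate check and scores about 8 days. The baseline is still ignored.

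**5. Size, by illustration only.** Assume first post-dose detection on Day 8, 14 and 28 in 60%, 25% and 15% of subjects. The mean is 0.60 x 8 + 0.25 x 14 + 0.15 x 28 = 12.5 days and the median is 8. Let a share q be elevated at entry, with a screening sample on Day -14 (literal time -13) or a first post-dose detection on Day 8.

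| q | Literal mean: 12.5(1 - q) - 13q | Post-baseline mean: 12.5(1 - q) + 8q |
|---|---|---|
| 5% | 11.2 | 12.3 |
| 10% | 9.95 | 12.05 |
| 20% | 7.4 | 11.6 |

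The median stays at 8 throughout. The literal minimum is -13. With the elevated subjects removed and only post-dose values used, the mean is 12.5 and the minimum 8.

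**6. Threshold wording.** The lead-in says above 5.5; the formula says 5.5 or higher. A subject whose highest post-baseline value is exactly 5.5 meets the event but is left out. The lead-in also gives no unit, in a section that presents laboratory values in SI units.

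**7. Calcium entry limit (secondary).** Protocol 6.2 exclusion 10 bars "Total corrected and/or ionized serum calcium" only from 1.5 x UNL. The SAP sets Grade 4 above 3.4 mmol/L corrected and above 1.8 mmol/L ionized. Assumed corrected UNLs of 2.50 to 2.65 give limits of 3.75 to 3.98; assumed ionized UNLs of 1.29 to 1.35 give 1.94 to 2.03. Exclusion 10 alone stays within the Grade 4 boundary only if UNL is at most 3.4/1.5 = 2.27 or 1.8/1.5 = 1.20 mmol/L.

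**The case against.** The best defence is that the lead-in already requires a post-baseline value above 5.5 and the label counts time from the start of treatment, so a programmer would naturally take the earliest post-baseline date. That is a fair reading, and it means negative times are a consequence of the literal wording, not a certainty. It also means that baseline elevation which does not persist or recur on treatment never enters the summary. It does not remove the Day 8 problem.

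A second defence is that baseline grade stays visible. The shift table runs from baseline grade to worst post-baseline grade using the ad hoc phosphate grades, changes from baseline are summarised by visit, and by-subject listings are planned (10.3.6). This stands: the number elevated at baseline can be found elsewhere. None of it corrects the onset summary.

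A reader might infer that the plan reports pre-existing elevation as drug toxicity. The documents do not support that. The SAP puts no toxicity label on this summary, and TEAEs must start or worsen on or after first dose, so an unchanged pre-existing elevation is not one.

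A reader might also infer that subjects with Grade 4 calcium could certainly enter. That goes too far. The UNL is assumed, and exclusion 8, whose exceptions name laboratory values, can be read as barring Grade 3-4 abnormalities. Exclusion 13 adds a discretionary screen.

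**Conclusion.** The point holds as a defect in one descriptive safety summary and should be corrected. The rule as written handles neither pre-dose dates nor baseline elevation. For a subject at or above 5.5 mg/dL before dosing who also exceeds 5.5 afterwards, it yields 1 day or less on the literal reading, or about Day 8 on the post-baseline reading. Neither is an onset time.

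The conclusion about entry rests on a UNL above 3.67 mg/dL; at 3.5 there is no overlap. The number of enrolled subjects affected is not in the documents. In the illustration the mean and minimum move while the median does not, and on the post-baseline reading the mean moves by less than a day. No test, error rate or named endpoint changes: the safety endpoint is the proportion of subjects with TEAEs and SAEs.

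Separately, the phosphate and calcium entry limits do not align with the contraindication statement in Protocol 3.3.3, the protocol and SAP grading, or Appendices E and G. Those sections need reconciling. Because enrolment is permanently halted, this does not change who enters the trial.

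**What to change.** In SAP 10.3.3:

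- Define the event as the earliest post-first-dose date with phosphate at or above 5.5 mg/dL, among subjects whose baseline is below 5.5 mg/dL.
- Use the same threshold and unit (5.5 mg/dL or more) in the lead-in sentence.
- Report the number of subjects with baseline at or above 5.5 mg/dL on a separate line.

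The conflict with SAP 9.2 then disappears, because no pre-dose date is used. The cost is about two sentences and one table row, from data already collected. The downside is slightly fewer subjects in the onset summary.

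As a documentary step, reconcile criterion 9g and exclusion 10 with Protocol 3.3.3, the grading in Protocol 9.1.3 and SAP 10.3.3, and Appendices E and G. Which limit should govern is a clinical decision for the sponsor.
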